### 3.4.1.2 Objective Response

Objective response rate (ORR) is defined as the proportion of subjects with a BOR of confirmed CR or confirmed PR. ORR will be estimated with a 95% CI using the exact probability method. For the expansion phase, an estimate of the difference in ORR between treatment groups will be reported and tested for significance with a Pearson chi-square test (or Fisher's exact test, as appropriate). Subjects that have missing overall response assessments will be considered non-responders, and will therefore be counted in the denominator, but not in the numerator of ORR.

#### 3.4.1.3 Disease Control

Disease control rate - 8 (DCR8) is defined as the proportion of subjects with a BOR of confirmed CR, confirmed PR, or SD (maintained for ≥ 8 weeks). A similar definition applies to DCR24. Duration of SD is defined as the time from randomization (dose expansion) / the first dose of IP (dose escalation) until the first documentation of disease progression or death due to any cause, whichever occurs first, and will allow for the protocol-defined disease assessment window of 3 days. DCR8 and DCR24 will be estimated with a 95% CI using the exact probability method. For the expansion phase, an estimate of the difference in DCR8 and DCR24 between treatment groups will be reported and tested for significance with a Pearson chi-square test (or Fisher's exact test, as appropriate).

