# **List of Abbreviations**

| Abbreviation | Definition   |  |  |
|--------------|--|--|--|
| AE           | adverse event  |  |  |
| AESI         | adverse event of special interest  |  |  |
| AZDD         | Astrazeneca Drug Dictionary  |  |  |
| BOR          | best overall response  |  |  |
| CI           | confidence interval  |  |  |
| CR           | complete response  |  |  |
| DC           | disease control  |  |  |
| DCR24        | disease control rate (SD maintained ≥ 24 weeks)                          |  |  |
| DCR8         | disease control rate (SD maintained ≥ 8 weeks)                           |  |  |
| DLT          | dose-limiting toxicity   |  |  |
| DR           | duration of response   |  |  |
| ECG          | electrocardiogram  |  |  |
| ECOG         | Eastern Cooperative Oncology Group                                       |  |  |
| EORTC        | European Organization for Research and Treatment of Cancer               |  |  |
| irCR         | immune-related complete response   |  |  |
| irNE         | immune-related not evaluable   |  |  |
| irPD         | immune-related progressive disease                                       |  |  |
| irPR         | immune-related partial response  |  |  |
| irRECIST     | immune-related Response Evaluation Criteria in Solid Tumors              |  |  |
| irSD         | immune response stable disease   |  |  |
| IV           | intravenous  |  |  |
| IXRS         | interactive voice/web response system                                    |  |  |
| MedDRA       | Medical Dictionary for Regulatory Activities                             |  |  |
| MTD          | maximum tolerated dose   |  |  |
| NCI CTCAE    | National Cancer Institute Common Terminology Criteria for Adverse Events |  |  |
| NE           | not evaluable  |  |  |
| NSCLC        | non-small cell lung cancer   |  |  |
| OR           | objective response   |  |  |
| ORR          | objective response rate  |  |  |
| OS           | overall survival   |  |  |
| PD           | progressive disease  |  |  |
| PD-1         | programmed cell death 1  |  |  |
| PD-L1        | programmed cell death ligand 1   |  |  |
| PFS          | progression-free survival  |  |  |
| PK           | pharmacokinetics   |  |  |
| PK-PD        | pharmacokinetics - pharmacodynamics                                      |  |  |
| PR           | partial response   |  |  |
| PRO          | patient-reported outcome   |  |  |
| Q2W          | every two weeks  |  |  |

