If a subject has two or more consecutive completely missed or non-evaluable assessments followed immediately by death or an assessment showing radiologic disease progression, then the subject will be censored for PFS. PFS will be censored at the date of randomization (dose expansion) / the first dose of IP (dose escalation) or the last progression-free disease assessment prior to the missed or non-evaluable assessments, whichever occurred last. If a subject has two or more consecutive missed or non-evaluable assessments followed by an assessment showing no radiologic disease progression, then the assumption will be that the subject did not progress during the missed or non-evaluable assessments. Two or more consecutive assessments is defined as  $\geq 17$  weeks (two disease assessments as per protocol plus a 1 week visit window to allow for a late assessment) after the last evaluable post-baseline disease assessment.

Subjects remaining on study without radiologic disease progression or death at the time of analysis will be censored for PFS at the date of their last adequate disease assessment. An adequate assessment is one that has recorded measurements for all target lesions and statuses for all non-target lesions defined at baseline (ie, the last non-missing or non-evaluable disease assessment). Additionally, a sensitivity analysis may be performed censoring PFS at the date of the last progression-free disease assessment prior to initiation of subsequent anticancer treatment.

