## 3.4.2 Additional Analyses of the Efficacy Endpoints

Disease Response will also be assessed based on an application of immune-related Response Evaluation Criteria in Solid Tumors (irRECIST) (Nishino et al, 2013) to investigator assessed tumor measurements. All new lesions meeting measureable criteria will be included in the Tumor Burden. Objective Response by irRECIST is defined as immune-related complete response (irCR) or immune-related partial response (irPR) with confirmation required occurring no fewer than 4 weeks after initial documentation of irCR or irPR. If an irPR or irCR that is pending confirmation is designated at an assessment followed by 1 or more non-evaluable assessments or assessments of irSD, response may be confirmed thereafter Disease Control - 8 by irRECIST is defined as confirmed irCR, confirmed irPR, or immune-related stable disease (irSD) (maintained for ≥ 8 weeks). A similar definition applies

to Disease Control - 24. Duration of irSD is defined as the time from randomization (dose expansion) / the first dose of IP (dose escalation) until the first documentation of disease progression or death due to any cause, whichever occurs first, and will allow for the protocoldefined disease assessment window of 3 days. Concordance/discordance between RECIST 1.1 and irRECIST disease assessment will be summarized in frequency table.

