Upon enrollment of 60 subjects in the dose-expansion phase, a final analysis will be performed. NoGo criteria will be met if the probability that the  $\delta$  exceeds the pre-specified

[figure not shown]
target of 20% is less than 10% (ie, NoGo:  $P[\delta > Target] < 10\%$ ). Go criteria will be met if the probability that the  $\delta$  exceeds the pre-specified target of 20% is more than 70% (ie, Go:  $P[\delta > Target] > 70\%$ ). For futility analyses, a response is defined as either a confirmed or unconfirmed CR or PR as per RECIST 1.1 and for the final analysis a response is defined as a confirmed CR or PR as per RECIST 1.1.

At interim analyses, efficacy and selected safety data will be summarized to assess the overall benefit-risk profile. The analysis populations to be used for the interim analysis are described below:

- As-treated with 17 weeks of potential follow up is defined as all subjects in the Astreated Population who have a baseline disease assessment and have an opportunity to be followed for at least 17 weeks (i.e., received the first dose of MEDI0680, durvalumab or nivolumab, whichever earliest, at least 17 weeks ago). The 17 weeks are to have at least 2 post-baseline disease assessments plus the one week visit window. This is the primary analysis population for the interim analysis of efficacy data.
- Response evaluable with 17 weeks of potential follow up is defined as all subjects in the As-treated Population who 1) have a baseline disease assessment; 2) have an opportunity to be followed for at least 17 weeks; and 3) have any post-baseline disease assessments or experience clinical PD/death. This is the secondary analysis population for the interim analysis of efficacy data.
- As-treated with 9 weeks of potential follow up is defined as all subjects in the Astreated Population who have a baseline disease assessment and have had an opportunity to be followed for at least 9 weeks. The 9 weeks are to have at least 1 post-baseline disease assessments plus one week visit window. This is the exploratory analysis population for the interim analysis of efficacy data.
- **As-treated Population**, as defined in section 3.2, is the primary analysis population for the interim analysis of safety data.

Figure 4-1 Decision Matrices for Continuous Monitoring

(MEDI0680 + Durvlumab vs Nivolumab: 10% false negative if effect = 20%)

[figure not shown]
[figure not shown]

Figure 4-2 Visual Joint Predictive Probability Operating Characteristics

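### DCR24 counts a subject whose week-24 scan shows progression as having stable disease maintained for at least 24 weeks

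*SAP*

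**What the plan says.** SAP Section 3.4.1.3 defines DCR8 as the "proportion of subjects with a BOR of confirmed CR, confirmed PR, or SD (maintained for ≥ 8 weeks"), and adds: "A similar definition applies to DCR24". The abbreviation list expands DCR24 as "disease control rate (SD maintained ≥ 24 weeks"). Duration of SD starts at randomization (expansion) or first dose (escalation) and runs "until the first documentation of disease progression or death due to any cause, whichever occurs first, and will allow for the protocol-defined" window of 3 days. Both rates get an exact 95% CI and, in the expansion phase, a test between arms.

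Four other places determine how this works in practice:

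- Section 3.4.1.1 requires only 6 weeks without radiological progression for a best overall response (BOR) of SD.
- Section 3.3.5.4 dates progression to the first test that shows it.
- The PFS censoring text explains its 17-week limit as "two disease assessments as per protocol plus a 1 week visit window to allow for a late assessment". Section 4 explains its shorter cut in the same way: "The 9 weeks are to have at least 1 post-baseline disease assessments plus one week visit window".
- Section 3.4.2 gives the irRECIST version of SD duration the same end point: "until the first documentation of disease progression or death due to any cause, whichever occurs first, and will allow for the" 3-day window.

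**The concern.** Progression is normally seen only at a scheduled scan. Time to documented progression therefore ends on the date of the scan that found it, not on the last date at which the disease was shown to be controlled. That is an ordinary convention for a duration. It fails as a pass/fail test when the threshold coincides with a scan date, because the scan that shows failure also supplies the last days needed to pass.

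At stake is the meaning of a reported rate. For subjects with SD, DCR24 would largely measure control shown at about week 16, plus the date on which the next failure was found. A reader of the rate and its exact CI would take it to be control at 24 weeks.

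**Working it through.** **Scan schedule implied by the SAP**

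- 17-week limit: (17 − 1) / 2 = 8 weeks per assessment.
- 9-week cut: 9 − 1 = 8 weeks to the first assessment.
- The two agree, so scans fall at weeks 8, 16 and 24 (days 56, 112 and 168). Week 24 is extrapolated from these cuts.

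**Threshold**

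24 × 7 = 168 days. Less the 3-day allowance, 168 − 3 = 165 days.

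**Subject with SD at weeks 8 and 16 and progression (PD) at the week-24 scan**

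BOR is SD, since more than 6 weeks have passed without progression. SD duration is the time to the PD date:

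| PD scan relative to day 168 | SD duration (days) | At least 165? | Counted in DCR24 | Last scan showing control |
|---|---|---|---|---|
| 7 days early | 161 | no | no | about day 112 |
| 3 days early | 165 | yes | yes | about day 112 |
| on time | 168 | yes | yes | about day 112 |
| 7 days late | 175 | yes | yes | about day 112 |

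Adding one day, as the SAP's other time formulas do, moves the edge by one day and changes nothing else.

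**The same check for DCR8**

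A subject whose first scan, at week 8, shows PD has BOR = PD and is excluded whatever the duration. DCR8 does not have the problem.

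**Size, on assumed inputs**

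The SAP states no median PFS and no share of non-responders among subjects who progress late. Assume exponential PFS, S(t) = 0.5^(t / median), with months converted to weeks by (365.25/12)/7. The share first found to have failed between the week-16 and week-24 scans is S(16) − S(24). Multiply by 0.55 to 0.75 for those not already counted as confirmed responders:

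| Assumed median PFS | S(16 wk) | S(24 wk) | Difference | × 0.55 | × 0.75 |
|---|---|---|---|---|---|
| 4 months | 0.529 | 0.384 | 0.144 | 7.9 points | 10.8 points |
| 6 months | 0.654 | 0.529 | 0.125 | 6.9 points | 9.4 points |
| 8 months | 0.727 | 0.620 | 0.107 | 5.9 points | 8.0 points |

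The range is about 6 to 11 points. In subjects:

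- Of 40: 0.059 × 40 = 2.4 to 0.108 × 40 = 4.3.
- Of 20: 0.059 × 20 = 1.2 to 0.108 × 20 = 2.2.

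For each set of inputs this is an upper limit, because it assigns every failure in the interval to a week-24 scan on day 165 or later. Deaths, unscheduled imaging and early scans that end SD before day 165 are already excluded by the current rule and reduce the figure.

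**The case against.** The strongest reply is that PFS, duration of response and SD duration all end at first documented progression, so the SAP is consistent. A subject with PD on day 168 is also progression-free on the Kaplan-Meier curve up to that day. This stands as a defence of the duration. It does not defend using the duration unchanged as the test of 24-week control. Nor does a gap between DCR24 and the PFS curve prove a fault: confirmed responders count toward DCR24 however short their response, so the two differ by design.

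Several stronger readings are tempting, and the SAP does not support them:

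- *A subject with SD at week 8, no further imaging and death at week 30 also passes.* Section 3.4.1.3 does not cite Table 3.2. But that table is titled for efficacy endpoints generally, and Section 3.3.5 says the handling of dropouts and missing data applies uniformly across the efficacy analyses. If the missed-assessment rule applies, this subject is censored at week 8 and does not pass. The fair criticism is an unclear cross-reference.
- *DCR8 is inflated in the same way.* It is not, because the BOR requirement blocks it.
- *The comparison between arms is biased.* Both arms follow the same rule, and nothing here shows a bias in the difference. What is shown is overstatement of each arm's rate.
- *SD should also end at subsequent anticancer treatment.* That is a separate choice. It would depart from the SAP's PFS definition, which counts progression regardless of such treatment.

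**Conclusion.** The point holds for DCR24 and its irRECIST counterpart. As written, a week-24 scan showing progression on day 165 or later yields a success for SD maintained for at least 24 weeks, and nothing else in the SAP overrides this. The classification error follows from the wording and the implied 8-weekly schedule; it does not depend on any PFS model.

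The size does depend on assumptions. With exponential median PFS of 4 to 8 months and 55% to 75% of the affected subjects not confirmed responders, each arm's rate is overstated by at most about 6 to 11 percentage points, or roughly 2 to 4 of 40 subjects and 1 to 2 of 20. These figures are limits on assumed inputs, and a reader should not take them as an estimate of the actual overstatement.

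Severity is minor to moderate. The powered comparison and the Go/NoGo rule use ORR only, but DCR24 is reported with an exact CI and tested between arms.

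**What to change.** In Section 3.4.1.3, and likewise in Section 3.4.2 for irRECIST, count SD as maintained for at least 24 weeks only if an evaluable assessment at or after week 24, less the allowed window, shows no progression and there is no earlier PD. State that the missed-assessment rule of Table 3.2 applies to SD duration. State also which window is meant, since the SAP uses 3 days for SD duration and 1 week in the PFS censoring text and Section 4. DCR8 needs no change for this reason.

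The change needs a few lines of SAP text and one derivation, using scans already scheduled. The costs are:

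- Reported DCR24 falls.
- A subject with SD whose week-24 scan is missed or done before the window opens, and who has no later progression-free scan, counts as not controlled. An example is a last progression-free scan on day 161 followed by PD at week 32. Some possible overstatement is thus exchanged for some possible understatement, so the number of such subjects should be reported beside the rate.

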#### 3.4.1.1 Best Overall Response

Best overall response (BOR) will be based on all post-baseline disease assessments that occur prior to the initiation of subsequent anticancer treatment. If re-treatment is permitted following an initial disease progression, a BOR will be reported separately for the re-treatment period. BOR will be summarized with the number and percentage of subjects for

the following categories: complete response (CR); partial response (PR); stable disease (SD); progressive disease (PD); and non-evaluable (NE).

At least 6 weeks from randomization (dose expansion) / the first dose of IP (dose escalation) first dose of IP must elapse without a radiological disease progression in order to assign a best overall response of SD. The definition of 6 weeks will allow for the protocol-defined disease assessment window of 3 days. Confirmation of PR and CR is required and must occur no fewer than 4 weeks after initial documentation of PR or CR. If a PR or CR that is pending confirmation is designated at an assessment followed by 1 or more non-evaluable assessments for CR or 1 or more non-evaluable assessments or assessments of SD for PR, response may be confirmed thereafter. Confirmation of PD is required in the dose escalation phase, but not the dose expansion phase. A confirmed PD will be a documented occurrence of a PD that is confirmed by a consecutive repeat assessment no fewer than 4 weeks later. A PD that occurs without follow-up scans to provide confirmation or only non-evaluable follow-up scans will also be considered a "confirmed" PD.

Concordance/discordance of disease assessment by investigator and derived disease assessment will be summarized in frequency table.

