#### 3.4.1.6 Progression-free Survival

Progression-free survival (PFS) is defined as the time from randomization (dose expansion) / the first dose of IP (dose escalation) until the first documentation of disease progression or death due to any cause, whichever occurs first, regardless of whether the subject receives subsequent anticancer therapy prior to progression. Subjects who have not progressed at the time of analysis will be censored at the time of the latest date of assessment from their last adequate progression free disease assessment. Censoring rules are presented in Table 3.2. PFS is defined in months as follows:

PFS (months) = (Date of PD/death or censoring – Date of randomization (dose expansion) / the first dose of IP (dose escalation) first dose of IP+1) / (365.25/12)

The median PFS and its 95% CI will be estimated using the Kaplan-Meier method. An 80% CI for median time *may* also be included.

For the expansion phase, the difference in PFS between treatment groups will be tested for significance with a logrank test. The hazard ratio for the two treatment groups with two-sided 95% CI will be estimated by a Cox proportional hazard model controlling for the prespecified stratification factors as explanatory variables in the model. The proportion of subjects progression free and alive at 6 months and associated 95% CI will be estimated using the Kaplan-Meier method.

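### DCR24 pairs a best response cut at subsequent anticancer treatment with a stable-disease duration that is not cut there

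*SAP*

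**What the plan says.** SAP 3.4.1.3 defines DCR8 as the "proportion of subjects with a BOR of confirmed CR, confirmed PR, or SD (maintained for ≥ 8 weeks"), and then adds "A similar definition applies to DCR24". The duration of SD starts at randomization (expansion) or first dose (escalation) and runs "until the first documentation of disease progression or death due to any cause, whichever occurs first, and will allow for the protocol-defined" assessment window of 3 days. For the expansion phase the same section has DCR8 and DCR24 compared between arms with a chi-square or Fisher test.

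The BOR inside that definition comes from 3.4.1.1: "Best overall response (BOR) will be based on all post-baseline disease assessments that occur prior to the initiation of subsequent anticancer treatment". The same section asks for at least 6 weeks, less the 3-day window, which "must elapse without a radiological disease progression in order to assign a best overall response of SD".

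Section 3.4.2 carries the duration rule over to irRECIST: "Duration of irSD is defined as the time from randomization (dose expansion) / the first dose of IP (dose escalation"), again ending only at progression or death.

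The SAP addresses subsequent therapy explicitly for one time-to-event endpoint. In 3.4.1.6, PFS is counted "regardless of whether the subject receives subsequent anticancer therapy prior to progression". Table 3.2 censors at subsequent treatment for sensitivity analyses only, and the text after it describes that as an optional PFS analysis. Section 3.4.1.5 takes the dates for duration of response from Table 3.2. Nothing links the duration of SD to that table.

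**The concern.** DCR24 has two components that treat subsequent anticancer treatment in opposite ways. The SD category must be earned before the switch, but the clock that decides whether SD was maintained keeps running after it. A tumor response on the next therapy is excluded, while the absence of progression on that therapy is credited to the randomized treatment.

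This matters because DCR24 is tested between randomized arms in an unblinded study (2.3), where treatment can stop for toxicity or other reasons without PD (2.2, 2.2.1). Switching before progression could differ by arm, and DCR24 would then partly reflect the next therapy. The rule is also open to two readings, so two programmers could derive different DCR24 values from the same data.

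**Working it through.** **Inputs.** Windows and thresholds come from 3.4.1.1 and 3.4.1.3: 6 weeks less 3 days = 39 days; 8 weeks less 3 days = 53 days (7.6 weeks); 24 weeks less 3 days = 165 days (23.6 weeks). The scan interval is inferred from 3.4.1.6, where two assessments plus a 1-week window make 17 weeks: (17 − 1)/2 = 8 weeks. Arm sizes are 40 and 20 (2.4).

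**The plan's own figure.** The SAP gives no assumption or power for DCR. Its only power figure is for ORR: 47.5% vs 21.5%, 40 vs 20 subjects, one-sided 0.10. With pooled p = (19 + 4.3)/60 = 0.388, the null SE is √(0.388 × 0.612 × (1/40 + 1/20)) = 0.1335 and the alternative SE is √(0.475 × 0.525/40 + 0.215 × 0.785/20) = 0.1211. Power = Φ((0.26 − 1.2816 × 0.1335)/0.1211) = 76.9%, against 76% stated. None of these inputs involves the duration of SD, so this figure does not depend on the point.

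**Applying the rules to constructed records.** *As written* takes the duration to PD. *With cut* takes it to the last scan before the new therapy. In every record the pre-switch scans show SD, so BOR is SD.

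| Pre-switch SD scans (week) | New therapy (week) | PD (week) | Duration as written / with cut | DCR8 as written / with cut | DCR24 as written / with cut |
|---|---|---|---|---|---|
| 8 | 10 | 40 | 40 / 8 | yes / yes | **yes / no** |
| 8, 16 | 18 | 40 | 40 / 16 | yes / yes | **yes / no** |
| 8, 16, 24 | 25 | 40 | 40 / 24 | yes / yes | yes / yes |
| 8 | 9 | 16 | 16 / 8 | yes / yes | no / no |
| 7 (early scan) | 7.5 | 20 | 20 / 7 | **yes / no** | no / no |

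DCR24 is exposed when a subject with SD switches without PD between about weeks 8 and 24 and is then not recorded as progressed or dead before the 24-week threshold. DCR8 changes only when the qualifying SD scan falls between about week 6 and week 8 less 3 days. A scan on the 8-week schedule already meets the DCR8 threshold.

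**Size per subject.** One reclassified subject moves DCR24 by 1/40 = 2.5 points (combination) or 1/20 = 5 points (nivolumab).

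**Assumed range, since the SAP gives no switching rate.** Zero to 4 such subjects of 40 shift the combination rate by 0 to 10 points (4/40); zero to 2 of 20 shift the nivolumab rate by 0 to 10 points (2/20). If switching occurs in one arm only, the between-arm difference moves by up to 10 points, in a direction set by which arm it is. With equal proportions, such as 4/40 and 2/20, it moves by 0.

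**The case against.** *Ignoring later therapy is a legitimate choice, and the SAP already makes it for PFS.* It is a legitimate choice, but the SAP states it for PFS only. DCR is built on a BOR that does the opposite, so the PFS policy cannot simply be assumed to apply.

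*The phrase defining SD as maintained could be read as carrying the BOR cut with it.* It could, but the explicit duration definition that follows does not say so. That ambiguity is itself a reason to add a sentence.

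*The cut has a cost of its own.* This stands. Anyone switching before the week-24 assessment, even after SD at week 16, becomes not controlled. If switching differs by arm, the cut also moves the comparison.

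*A reader might infer that DCR24 is overstated by several points.* The documents do not support that. They give no switching rate, no time to PD and no PFS on later therapy. Even under an assumed model the inference fails. Take subjects in SD at week 8, a median of 5 months (21.7 weeks) to PD from then, and 8-weekly scans. With no switching, DCR24 is 2^(−16/21.7) = 0.60. With 5%, 10% or 20% set to switch between weeks 8 and 24, and a median PFS of 4 to 9 months on the next therapy, the rule as written gives 0.59 to 0.62, close to the no-switching value. The cut gives 0.57, 0.54 and 0.48. The gap separates two definitions; it does not measure bias against a known truth.

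*A reader might also extend the point equally to DCR8.* The scan schedule rules that out except for early scans.

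**Conclusion.** The point holds for DCR24 by RECIST 1.1 as an internal inconsistency: BOR stops at subsequent treatment, the duration of SD does not, and no other section reconciles them. It extends to DCR24 by irRECIST on the reading that the BOR restriction in 3.4.1.1 carries over. Section 3.4.2 repeats the uncut duration but does not restate that restriction.

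The firm size is 2.5 or 5 points of DCR24 per reclassified subject. How many there would be, and which arm would gain, cannot be determined from the SAP; the 0-to-10-point range rests on assumed counts. DCR8 is affected only by early qualifying scans. The sample size rests on ORR, and ORR, its power and the Go/NoGo rules of section 4 do not use the duration of SD. The correction is worth making before analysis because DCR24 is formally compared between arms, but it does not touch the main conclusion of the trial.

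**What to change.** Add one sentence to 3.4.1.3 and one to 3.4.2: for disease control, when subsequent anticancer treatment starts before PD, the duration of SD (irSD) is taken to the last adequate progression-free disease assessment before that treatment, and SD counts as maintained for 8 or 24 weeks only if that date reaches the threshold less the 3-day window. In 3.4.2, also state that irRECIST best response uses only assessments before subsequent treatment, if that is intended.

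Keep the uncut version, in line with the PFS definition, as a sensitivity analysis, so that the effect of the choice is visible in each arm.

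The cost is small. The start date of subsequent treatment is already needed for the BOR rule and for the sensitivity censoring in Table 3.2, and 3.4.1.6 already defines an adequate assessment. The downside is that DCR24 may be somewhat lower, and subjects who switch before the week-24 assessment count as not controlled. The sample size does not change.
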